### 3.4 CRITERIA FOR REMOVAL FROM PROTOCOL THERAPY AND OFF STUDY CRITERIA

Prior to removal from off study , effort must be made to have all subjects complete a safety visit approximately 30 days following the last dose of study therapy.

#### 3.4.1 Criteria for removal from protocol therapy.

- The patient refuses to continue therapy.
- At the principal investigator's discretion, if the PI deems the patient to be at an unacceptable risk/benefit ratio to remain on the study.
- PI of the patient's primary transplantation protocol requests removal.
- Participant becomes pregnant

#### 3.4.2 Off Study Criteria

- Completed either D+100 post-transplant evaluation, 6 month post-transplant evaluation, or 6 months evaluation after completion of ECP)
- Participant requests to be withdrawn from study
- Death
- PI decision to end this study

#### 3.4.3 Off Protocol Therapy and Off Study Procedure

Authorized staff must notify Central Registration Office (CRO) when a subject is taken off-study. A Participant Status Updates Form from the web site (<http://home.ccr.cancer.gov/intra/eligibility/welcome.htm>) main page must be completed and sent via encrypted email to: NCI Central Registration Office [[contact]](mailto:[contact]).

## 4 CONCOMITANT MEDICATION

There are no specific restrictions on the use of any other agents or procedures deemed necessary for the ongoing care of the patients on this study.

## 5 BIOSPECIMEN COLLECTION

### 5.1 CORRELATIVE STUDIES FOR RESEARCH

#### 5.1.1 Biomarker Assays

One (1) 10 mL Sodium-Heparin/Green-top tube, and up to five (5) 8 mL CPT/Sodium-Heparin/Red+Green-top tubes will be sent via escort to ETIB Preclinical Development and Clinical Monitoring Facility (PDCMF) (Bldg 10, Room 12C216). All enrolled patients will have this blood work drawn at time points as detailed in the study calendar (see Section **3.3**). TIM3, IL-6, Reg-3-a, ST2, LPS-BP, Nitrate, TNFR1, IL-2Ra, CXCL10, and HGF will initially be

studied. Assay will be either by Luminex Microbead (Luminex, Austin, TX) or enzyme linked immunosorbent assay (ELISA) using commercially available reagents and protocols.

## 5.2 STORAGE, TRACKING AND DISPOSITION

### 5.2.1 Storage/Tracking in the Preclinical Development and Clinical Monitoring Facility (PDCMF)

- Samples will be ordered in CRIS and tracked through a Clinical Trial Data Management system. Should a CRIS screen not be available, the CRIS downtime procedures will be followed. Samples will not be sent outside NIH without IRB notification and an executed MTA.
- Normal donor and patient blood and tissue samples, collected for the purpose of research under IRB approved protocols of the Experimental Transplantation and Immunology Branch, may be archived by the ETIB Preclinical Development and Clinical Monitoring Facility (PDCMF). All data associated with archived clinical research samples is entered into the ETIB PDCMF's Microsoft Excel databases on frozen cells and plasma. These databases are stored on the NCI group drive in the ETIB 'PRECLINSERVICE' folder. Access to this folder is limited to PDCMF staff and ETIB clinical staff, requiring individual login and password. All staff in the PDCMF laboratory receive annually updated NIH/CIT training and maintain standards of computer security.
- The data recorded for each sample includes the patient ID, trial name/protocol number, date drawn, treatment cycle/post-transplant time point, cell source (e.g., peripheral blood, lymphapheresis, mobilized peripheral blood stem cells, marrow, pleural fluid) as well as box and freezer location. Patient demographics that correlate treatment outcomes and therapies with the samples can be obtained only through the NCI/ETIB clinical records. As of January 2007, all newly received samples will receive a unique bar code number, which is included in the sample record in the PDCMF database. Only this bar code is recorded on the sample vial and the vials will not be traceable back to patients without authorized access to the PDCMF database. All non-coded samples previously archived will be stripped of identifiers prior to distribution for any use other than as a primary objective of the protocol under which they were collected.
- Samples are stored in locked freezers. All samples will be labeled solely with a bar code (which includes the date, and serially determined individual sample identifier). The key will be available to a restricted number of ETIB investigators and associate investigators on the protocol. Coded samples will be stored frozen at -20, -80° or liquid nitrogen vapor phase to -180 C according to stability requirements in a single location under the restricted control of the PDCM Facility of ETIB.
- Access to samples from a protocol for research purposes will be by permission of the Principal Investigator of that protocol in order to be used (1) for research purposes associated with protocol objectives for which the samples were collected, or (2) for a new research activity following submission and IRB approval of a new protocol and consent, or (3) for use only as unlinked or coded samples under the OHSRP Exemption Form guidelines stipulating that the activity is exempt from IRB review. Unused samples must be returned to the PDCMF laboratory.

- Samples, and associated data, will be stored permanently unless the patient withdraws consent. If researchers have samples remaining once they have completed all studies associated with the protocol, they must be returned to the PDCMF laboratory.
- These freezers are located onsite at the Preclinical Service laboratory (12C216) or in ETIB common equipment space (CRC/3-3273).

### 5.2.2 Protocol Completion/Sample Destruction

- Once research objectives for the protocol are achieved, researchers can request access to remaining samples, providing they have both approval of the Principal Investigator of the original protocol under which the samples or data were collected and either an IRB approved protocol and patient consent or OSHRP approval.
- The PDCMF staff will report to the Principal Investigators any destroyed samples, if samples become unsalvageable because of environmental factors (ex. broken freezer or lack of dry ice in a shipping container), lost in transit between facilities or misplaced by a researcher. The Principal Investigators will annually report this information to the IRB and the NCI Clinical Director, and the office of the CCR, NCI.
- The PI will report destroyed samples to the IRB if samples become unsalvageable because of environmental factors (ex. broken freezer or lack of dry ice in a shipping container) or if a patient withdraws consent. Samples will also be reported as lost if they are lost in transit between facilities or misplaced by a researcher. Freezer problems, lost samples or other problems associated with samples will also be reported to the IRB, the NCI Clinical Director, and the office of the CCR, NCI.

## 6 DATA COLLECTION AND EVALUATION

### 6.1 DATA COLLECTION

An enrollment log will be maintained in the regulatory binder/file which is the only location of personal identifiers with unique subject identification number.

No IND agents, equipment or procedures are being used in this study.

Study data will be maintained, entered, and audited for accuracy in the C3D Database by the research nurse(s) and data managers assigned to the study.

Only adverse events related to the ECP procedure will be collected as part of this study. All other AEs will continue to be collected on the patient's primary transplant protocol. Since AEs collected are only ECP related, baseline AEs will only be collected on patient's that proceed with ECP. The baseline will be considered the immediate time before their first ECP treatment.

The PI will be responsible for overseeing entry of data into an in-house password protected electronic system (C3D) and ensuring data accuracy, consistency and timeliness. The principal investigator, associate investigators/research nurses and/or a contracted data manager will assist with the data management efforts. All data obtained during the conduct of the protocol will be kept in secure network drives or in approved alternative sites that comply with NIH security standards.

Primary and final analyzed data will have identifiers so that research data can be attributed to an individual human subject participant.

All AEs, including clinically significant abnormal findings on laboratory evaluations, regardless of severity, will be followed until return to baseline or stabilization of event. Patients will be followed for adverse events for at least 30 days after removal from study treatment or until off study, whichever comes first.

An abnormal laboratory value will be considered an AE if the laboratory abnormality is characterized by any of the following:

- Results in discontinuation from the study
- Is associated with clinical signs or symptoms
- Requires treatment or any other therapeutic intervention
- Is associated with death or another serious adverse event, including hospitalization.
- Is judged by the Investigator to be of significant clinical impact
- If any abnormal laboratory result is considered clinically significant, the investigator will provide details about the action taken with respect to the test drug and about the patient's outcome.

**End of study procedures:** Data will be stored according to HHS, FDA regulations and NIH Intramural Records Retention Schedule as applicable.

**Loss or destruction of data:** Should we become aware that a major breach in our plan to protect subject confidentiality and trial data has occurred, the IRB will be notified.

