ECP utilizing the Therakos system has an established safety profile with over 500,000 treatments performed to date (Therakos User Manual 2001). The only absolute contraindication for ECP is in patients who cannot tolerate extracorporeal volume loss (severe heart failure, hypotension, sepsis) or patients with coagulation disorders. In addition, methoxsalen (Oxsoresalen-Ultra®), the FDA-approved 8-MOP compound used with the Therakos device, is contraindicated in patients with idiosyncratic reactions to psoralen compounds, those with a history of light-sensitive disease (such as patients with systemic lupus erythematosus with photosensitive disease), or those with aphakia. Serious side effects with the procedure itself have rarely been reported, most of which are related to hypotension secondary to changes in extracorporeal volume. A large, multicenter survey focusing on immediate adverse effects of therapeutic apheresis reported no adverse events from a total of 79 ECP procedures with the majority of these procedures done using the Therakos system^47. More recently, a phase II, randomized, controlled trial did not show significant differences in safety outcomes between the arm receiving ECP therapy for chronic graft versus host disease and the control-arm. The overall rates of infections (53.1% versus 44%), diarrhea (20.4% versus 20%), and nausea (18.4% versus 12%) were not significantly different between those receiving ECP and steroids versus steroids alone, while anemia occurred more frequently in those receiving ECP treatment (24.5% versus 6%;  $p = 0.02$ ). In clinical practice, anemia in patients receiving ECP therapy can be seen and is most likely attributed to small volume blood loss over repeated procedures. In contrast to other GVHD therapies, studies have found that ECP therapy does not have immunosuppressive effects and therefore does not add to the risk for opportunistic infections. Secondary malignancies have not been associated with ECP; however, photosensitivity may occur and patients are instructed to take standard precautions as it relates to sun exposure. Fatigue, pruritus and fevers have also been reported during or after ECP treatment. Because intravenous (IV) access is required, patients are at risk for catheter-related complications including infection and thrombosis.

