### 1.2.6 Background and Rationale: Summary

Current therapy of acute GVHD, especially steroid refractory disease, is unsatisfactory in a majority of patients due to both limited effectiveness and highly variable morbidity of many of the treatments. No single treatment regimen has been shown to consistently alter outcomes. Immunosuppression and subsequent infection contribute to the poor outcome steroid refractory disease. ECP is an attractive treatment modality due to its unique mechanism of action and low toxicity profile. Combining ECP with other treatments for GVHD is likely feasible, tolerable, and, based on prior experiences in the literature, not be expected to increase the toxicity of treatment. The potential of ECP to improve outcomes in this setting, either alone or in combination, has been incompletely explored. Recently described acute GVHD biomarkers have the potential to improve future prediction of refractory disease and therapeutic outcome of the varied treatments currently in use. Data will be collected on the procedure specific complications of ECP in combination with other therapies currently in use for acute GVHD.

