#### 3.2.2 ECP Procedure

Patients who will undergo ECP will be treated according to the standard operating procedure of the Clinical Center Department of Transfusion Medicine. The procedure may be done in a hospital room, an outpatient department, or in DTM

The UVAR will be used to perform therapeutic ECP under the direction of a Department of Transfusion Medicine (DTM) physician, in accordance with specific NIH Clinical Center Protocols, and the Medical Chief of Blood Services Section (BSS). Unless otherwise stated, the apheresis staff will adhere to the manufacturer's recommendations when performing ECP.

Registered Nurses will perform ECP as ordered by DTM physicians in the Clinical Research Information System (CRIS). The Operator's Manual for the UVAR and the directions for use with the apheresis kit will be followed at all times.

If the patient lacks adequate existing venous access for ECP, they may need to have a catheter placed by Interventional Radiology or the VAD Service.

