### 9.4.2 Related to Methoxsalen Administration and ECP Procedure

Potential risks of methoxsalen and the ECP procedure are described in Section 10 and the consent form. There may also be unexpected side effects. All subjects will be carefully monitored for side effects. In addition, if additional intravenous access is required, there will be risks associated with catheter insertion and maintenance including bleeding infection, pain, and rarely death.

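### The adverse-event baseline falls after a catheter placed for ECP, so insertion complications arising before the first ECP are filed as baseline or missing from the ECP safety data

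*Combined protocol and SAP*

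**What the plan says.** Section 6.1 (Data Collection) restricts what this study gathers: "Only adverse events related to the ECP procedure will be collected as part of this study". The rest is left elsewhere: "All other AEs will continue to be collected on the patient's primary transplant protocol". It adds that "baseline AEs will only be collected on patient's that proceed with ECP", and sets the reference time: "The baseline will be considered the immediate time before their first ECP treatment". Events are then followed until they return to that baseline or stabilise.

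The calendar in 3.3 puts its ECP Adverse Events row in the two ECP-only columns: one at the first ECP of each treatment month, the other six months after the last ECP. There is no entry at catheter placement or at the decision to use ECP.

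On access, section 3.2.2 (ECP Procedure) says of patients whose existing access is inadequate that "they may need to have a catheter placed by Interventional Radiology or the VAD Service". Section 9.4.2, on the risks of methoxsalen and the ECP procedure, says that in this case "there will be risks associated with catheter insertion and maintenance including bleeding infection, pain, and rarely death". Section 1.2.5 says that, because intravenous access is required, "patients are at risk for catheter-related complications including infection and thrombosis". Section 10.2, on the photopheresis procedure, attributes a small hazard of infection and pain to venous access.

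Section 1.2.6 makes the commitment that these rules should serve: "Data will be collected on the procedure specific complications of ECP in combination with other therapies currently in use for acute GVHD".

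**The concern.** If a patient lacks access at the outset, the catheter goes in before the first ECP. The adverse-event clock in 6.1 starts only when that ECP is about to begin. A bleed, early line infection or clot already present at that moment becomes part of the reference state, although the protocol itself names it as a risk of receiving ECP.

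A patient who has the catheter placed and then never starts ECP has no baseline record and no scheduled ECP adverse-event assessment. This gap may depend on outcome: section 2.1.2.2 lists uncontrolled infection, uncorrectable coagulopathy and inability to maintain access among the contraindications to ECP, so a catheter complication could itself prevent the first treatment.

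At stake is whether the data promised in 1.2.6 are complete. The rationale for adding ECP to other treatments leans on its low toxicity (1.2.5, 1.2.6), and the misclassification runs in one direction, towards fewer ECP complications.

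**Working it through.** The plan attaches no rate, sample size or precision to ECP safety, so there is no figure to reproduce. The check is mainly a reading of the sections against each other.

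1. **Is access part of the procedure?** No text formally defines which events are related to the ECP procedure. Catheter placement appears under the procedure heading in 3.2.2, its complications under the procedure-risk heading in 9.4.2, and access hazards again under the photopheresis procedure in 10.2. All three point the same way.

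2. **Patient who proceeds.** Catheter placed, complication, baseline, first ECP. Under 6.1 a complication present at the third step is a baseline finding.

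3. **Patient who does not proceed.** Catheter placed, complication, no ECP. Section 6.1 takes no baseline record and 3.3 schedules no ECP adverse-event visit.

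4. **Events outside the gap.** A line infection or thrombosis arising after the first ECP is post-baseline and can be collected. So can complications of a catheter placed after ECP has begun. The affected window runs only from initial placement to first ECP.

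5. **Other routes.** Section 6.1 leaves other events to the primary transplant protocol, whose rules are not in these documents. Section 7.2.1 requires deaths not due to progressive disease to be reported within 7 days. Section 7.2.2 tabulates all serious and all Grade 5 events whatever their attribution. Among non-serious events, 7.2.2 omits Grade 1. It takes Grade 2 only if unexpected and at least possibly related to the research; infection, bleeding and pain from a catheter are named risks, hence expected. It takes Grade 3 and 4 only if at least possibly related, a judgement that filing the event as baseline makes less likely. None of these routes labels an event as an ECP harm.

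6. **Scale, by assumption only.** The documents give neither the share of ECP patients needing a new catheter (s) nor the chance of a complication before the first ECP (r). Assume s from 25% to 100% and r from 1% to 10%. Expected events before baseline = n × s × r; chance of at least one = 1 − (1 − s × r)^n. The sizes 22, 34 and 100 come from section 8; the 5 enrolled come from 3.1, which does not say how many received ECP.

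| n with ECP | Expected events | Chance of at least one |
|---|---|---|
| 5 (if all had ECP) | 5 × 0.25 × 0.01 = 0.01 to 5 × 1 × 0.10 = 0.5 | 1% to 41% |
| 22 | 22 × 0.25 × 0.01 = 0.06 to 22 × 1 × 0.10 = 2.2 | 5% to 90% |
| 34 | 34 × 0.25 × 0.01 = 0.09 to 34 × 1 × 0.10 = 3.4 | 8% to 97% |
| 100 | 100 × 0.25 × 0.01 = 0.25 to 100 × 1 × 0.10 = 10 | 22% to over 99% |

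The width of these ranges shows that the documents do not fix the size.

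**The case against.** The strongest reply is that 6.1 collects by relatedness, not by date. Only the baseline record is confined to patients who proceed, and nothing forbids an investigator from recording an earlier event judged related to ECP. The calendar lists visits; it does not exclude events between or before them. This stands to the extent that the text is a gap and not a prohibition. But with baseline defined as it is and no assessment scheduled earlier, following the rule as written files the event as pre-existing or never prompts for it.

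A reader might infer that the gravest cases vanish altogether. The documents do not support that. A death, or a bleed, clot or infection severe enough to stop ECP, is likely to be serious under 7.1.6 and so reaches the IRB through 7.2. What is missing for such events is the link to ECP; the events most exposed are non-serious. A reader might also infer that catheter complications in general go uncounted. They do not: treatment may run to seven months (3.2.1), and anything arising after the first ECP is collectable.

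It is also fair to say that safety is neither a primary nor a secondary objective, that section 8 plans no ECP complication rate, and that 3.1 reports 5 patients, all off study, with accrual on hold. These points lower the weight and urgency. They do not remove the mismatch with 1.2.6.

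**Conclusion.** The point holds in a narrow form. An insertion complication arising between initial placement of a catheter for ECP and the first ECP would be entered as baseline, or be absent from this study's ECP adverse-event data if ECP never starts. This rests on reading venous access placed for ECP as part of the procedure, as the section headings do although no definition says so.

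The likely direction is some under-counting of early access complications. The amount cannot be derived, because the ranges above rest on assumed shares and rates. A reader might set them against the survey in 1.2.5 that found no adverse events in 79 ECP procedures and infer that one or two catheter events would overturn the safety picture. That comparison is not available: the survey counted procedures and immediate apheresis effects, whereas the events here are counted per patient and concern catheter placement.

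With so few patients enrolled, the practical importance lies in how those 5 are reported and in any reopening. It is a cheap clarification of data collection and raises no question about how patients should be treated.

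**What to change.** In 6.1, state that venous access placed specifically for ECP counts as part of the ECP procedure for adverse-event purposes. Set baseline, and start ECP adverse-event collection, at the earlier of that placement and the first ECP. Leave relatedness to the investigator's judgement under the reasonable-possibility standard in 7.1.2; a catheter complication should not be attributed to ECP automatically.

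Include patients who had a catheter placed for ECP but never started, and report against a denominator that covers them: patients who had a catheter placed for ECP or received at least one ECP. Add a matching footnote to the ECP Adverse Events row in 3.3. For the 5 patients already off study, apply the same definition when their data are reported, from the chart where it allows.

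The cost is a few sentences, a footnote and slightly more chart abstraction. The ECP complication count may look somewhat less favourable. Nothing in the change touches treatment or the choice of access.

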## 6.2 RESPONSE CRITERIA

### 6.2.1 Recording of Steroid Dose

Steroid dose will be recorded in prednisone mg equivalency.

